9.2. Clinical Laboratory Evaluations

Laboratory tests identified in Appendix 1 in the protocol will be performed at times defined in the Schedule of Activities, Section 1.3 of the protocol. Clinical chemistry, hematology, and coagulation parameters will be reported based on the International System of Units (SI). All abnormal laboratory results will be evaluated by the Investigator as either clinically significant or not clinically significant.

Observed values and changes from baseline for hematology, clinical chemistry, urinalysis, and inflammatory biomarker laboratory evaluations will be summarized by cohort at each scheduled visit (Baseline/Day 1, Day 15, Day 29/Early Termination, and Day 43/End of Study) and most extreme change.

Box plots will be produced by visit and treatment for the recorded values of Erythrocyte Sedimentation Rate, C-reactive Protein, and Fecal Calprotectin. As well, line plots of the mean change from baseline of these three tests at each visit will be produced by treatment.

The number and percentage of patients experiencing treatment-emergent graded toxicities will be summarized by cohort and severity grade per the National Cancer Institute Common Terminology Criteria for Adverse Events (CTCAE) version 4.0.3. For each parameter, a patient will only be counted once using the worst-case value among all post-baseline timepoints. Laboratory toxicity will be summarized by incidence of CTCAE grade 3 and CTCAE grade 4 values for measures with a corresponding CTCAE grade. For measures without a corresponding CTCAE grade, incidence of 2.5 to < 5.0 X upper or lower limit of normal and ≥ 5.0 X upper or lower limit of normal cohort by cohort. Patients with missing values post-baseline will be excluded from the summary. The denominator for percentages will be the number of patients with at least one post-baseline assessment for the laboratory parameter being displayed. Separate summary counts will be prepared for parameters with bi-directional toxicity grading with “high/hyper” conditions depending on the maximum post-baseline value and the “low/hypo” conditions depending on the minimum post-baseline value.

All laboratory parameters will be provided in patient data listings for all enrolled patients.

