5.2 Exclusion Criteria

An individual for whom any of the following criteria apply will be excluded from participation in this study:

Gastrointestinal-related Medical Conditions

1. At the time of screening, patient has a diagnosis of an IBS subtype other than IBS-D, based on Rome IV criteria (CCI [REDACTED]). Based on stool patterns on days that the patient experiences symptoms, other IBS subtypes are defined as follows:
 - a. IBS-C: hard or lumpy stools \geq 25% of bowel movements and loose or watery stools \leq 25% of bowel movements;
 - b. IBS-M: hard or lumpy stools \geq 25% of bowel movements and loose or watery stools \geq 25% of bowel movements;
 - c. IBS-U: hard or lumpy stools \leq 25% of bowel movements and loose or watery stools \leq 25% of bowel movements.
2. Patient has a history of inflammatory or immune-mediated GI disorders including (but not limited to) inflammatory bowel disease (i.e., Crohn's disease, ulcerative colitis, microscopic colitis, and celiac disease).
3. Patient has had an episode of diverticulitis within 3 months prior to Screening.
4. Patient has a history of intestinal obstruction, stricture, toxic megacolon, GI perforation, fecal impaction, gastric banding, bariatric surgery, adhesions, ischemic colitis, or impaired intestinal circulation (e.g., aortoiliac occlusive disease).
5. Patient has any of the following surgical history:
 - a. Cholecystectomy with ANY history of post-cholecystectomy biliary tract pain. A successful cholecystectomy with no postoperative biliary tract pain is not exclusionary;
 - b. Any abdominal surgery within the 3 months prior to Screening;
 - c. Major gastric, esophageal, hepatic, pancreatic, or intestinal surgery (appendectomy, hemorrhoidectomy, or polypectomy greater than 3 months post-surgery are allowed).
6. Patient has a history or current evidence of laxative abuse.

Other Medical Conditions

7. Patient has a history of a cardiovascular event, including stroke, myocardial infarction, congestive heart failure, or transient ischemic attack within 6 months prior to Screening.
8. Patient has a history of malignancy within 5 years prior to Screening (except squamous and basal cell carcinomas of the skin and cervical carcinoma *in situ*).
9. Patient has a history of alcohol abuse or binge drinking.

10. Patient has uncontrolled hypertension, defined as systolic blood pressure > 180 mmHg or a diastolic blood pressure > 100 mmHg at the time of Screening.

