9.4.2.2 Clinical Laboratory Evaluations

Laboratory data will be listed for all patients. Laboratory data will be reviewed by the Investigator as they become available. All abnormal laboratory results will be evaluated by the Investigator as either clinically significant or not clinically significant.

Descriptive summaries of clinical laboratory results will be presented by date and time of collection. The number and percentage of patients experiencing treatment-emergent graded toxicities will be summarized by treatment arm and severity grade. Laboratory toxicity shifts from baseline to post-baseline assessments will be summarized by treatment arm. Changes from baseline in laboratory tests will be summarized for each treatment arm.

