9.3. Other Safety Evaluations

For electrocardiogram and vital signs results, Marked Abnormality will be defined in the following sections. Should a patient have a Markedly Abnormal result at baseline, only those

Sponsor: Boston Pharmaceuticals, Inc.
Protocol Number: BOS-589-201
Version and Date: Version 1.2 12NOV2020

post-baseline results that are at least 1 grade more extreme than the baseline grade will be considered as a Marked Abnormality.

9.3.1. 12-Lead Electrocardiogram

12-lead electrocardiograms (ECGs) will be assessed as specified in the Schedule of Activities in Section 1.3 of the protocol. The following ECG parameters will be collected: PR interval (milliseconds [msec]), QRS interval (msec), QT interval (msec), QT interval corrected for heart rate (QTc) (msec), and Ventricular Rate (beats/min). ECG parameters and ECG evaluation will come directly from the database and will not be calculated during analysis.

Observed values and changes from baseline for ECG parameters will be summarized at each scheduled visit (Screening and Day 29/ Early Termination) by cohort and overall.

Observed and change from baseline values on Day 29 in QTc status categorized as markedly abnormal (defined in the table below) or not will be summarized.

QTc Measure	Markedly Abnormal Criteria
Observed	450–480 msec, inclusive [CTCAE grade 1] 481–500 msec, inclusive [CTCAE grade 2] > 500 msec [CTCAE grade 3 or higher]
Change from Baseline	31–60 msec, inclusive, increase from baseline >60 msec increase from baseline

If triplicate measures were taken at a single time point, the average will be summarized. All ECG data will be presented in a by patient data listing for all enrolled patients. Measures meeting the markedly abnormal criteria will be flagged in the listing.

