9.3.3. Vital Signs

Vital signs include: pulse rate (beats/min), respiratory rate (breaths/min); temperature (degrees Celsius [°C]); systolic and diastolic blood pressure (millimeters of mercury [mmHg]); height, weight (kg), and BMI (derived).

Observed values and changes from baseline for vital signs will be summarized at by cohort and overall for each scheduled visit (Baseline/Day 1, Day 8, Day 15, Day 22, Day 29, and Day 43) and most extreme change.

Summaries of pulse rate, temperature, systolic blood pressure, and diastolic blood pressure will be based on markedly abnormal criteria defined below:

Vital Sign	Markedly Abnormal Criteria
Pulse rate (beats/min)	< 60 beats/min ≥ 100 beats/min
Temperature (°C)	≤ 35 °C ≥ 38 °C
Systolic blood pressure (mmHg)	120-139 mmHg, inclusive (CTCAE grade 1) 140–159 mmHg, inclusive (CTCAE grade 2) ≥ 160 mmHg (CTCAE Grade 3)
Diastolic blood pressure (mmHg)	80–89 mmHg, inclusive (CTCAE grade 1) 90–99 mmHg, inclusive (CTCAE grade 2) ≥ 100 mmHg (CTCAE grade 3)

Incidence of post-baseline markedly abnormal worst-case values will be presented. For pulse rate and temperature, both high and low values will be presented separately such that patients can be counted in both categories.

All vital signs data will be presented in patient data listings for all enrolled patients. Markedly abnormal vital sign values will be flagged as such in the vital signs listing.

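### Laboratory toxicities are counted as treatment-emergent without reference to baseline, the protocol's shift summary is not in the SAP text, and the vital-sign baseline rule is undefined for pulse and temperature

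*SAP*

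**What the plan says.** **Laboratory data.** Protocol 9.4.2.2 commits to three outputs by treatment arm: counts of treatment-emergent graded toxicities, a shift summary ("Laboratory toxicity shifts from baseline to post-baseline assessments will be summarized by treatment arm"), and changes from baseline.

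SAP 9.2 keeps the first: "The number and percentage of patients experiencing treatment-emergent graded toxicities will be summarized by cohort and severity grade per the National Cancer Institute" criteria (CTCAE). The counting rule is "For each parameter, a patient will only be counted once using the worst-case value among all post-baseline timepoints". On display it says "Laboratory toxicity will be summarized by incidence of CTCAE grade 3 and CTCAE grade 4 values for measures with a corresponding CTCAE grade"; tests without a CTCAE grade get two bands, 2.5 to below 5.0 times and at least 5.0 times the limit of normal. On percentages: "The denominator for percentages will be the number of patients with at least one post-baseline assessment for the laboratory parameter being displayed". Changes from baseline and most extreme change are also kept. No shift summary is mentioned. SAP 3.2, which records departures from the protocol, names only the weekly-responder endpoint and the custody of the randomization file.

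**ECG and vital signs.** SAP 9.3 does condition on baseline. If the baseline is markedly abnormal, only "post-baseline results that are at least 1 grade more extreme than the baseline grade will be considered as a Marked Abnormality". SAP 9.3.1 grades observed QTc and SAP 9.3.3 grades blood pressure, each in three steps. Pulse (below 60, or 100 and above) and temperature (35 °C or lower, or 38 °C and above) have one low and one high cut-off and no grade. Protocol 5.2 excludes patients with "systolic blood pressure > 180 mmHg or a diastolic blood pressure > 100 mmHg at the time of Screening".

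**The concern.** Safety and tolerability relative to placebo is a primary objective. The named safety endpoints are adverse-event measures, so the laboratory and vital-sign tables are supporting evidence; but there is no safety monitoring committee (SAP 3.5), and these end-of-study tables are where a pattern across cohorts would be looked for.

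Adjacent sections treat baseline in opposite ways. SAP 9.2 attributes to the treatment period abnormalities that may have been there before the first dose. SAP 9.3 tries to remove pre-existing abnormalities, but its rule depends on a grade that two of the four tabulated vital signs lack. The shift summary would have separated new from existing laboratory toxicity and shown new grade 1 and 2 changes, which no categorical laboratory table described in the SAP displays.

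**Working it through.** The plan states no figure on this point, so there is none to reproduce. The check applies the rules as written.

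**1. Laboratory counts.** Let G0 be the baseline grade and Gmax the worst post-baseline grade.

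- SAP 9.2 counts a patient if Gmax ≥ 3.
- A treatment-emergent rule would count a patient if Gmax ≥ 3 and Gmax > G0.
- The two differ for patients with Gmax ≥ 3 and G0 ≥ Gmax: unchanged at grade 3 or 4, or improved from 4 to 3. The same holds for the limit-multiple bands.

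The treatment-emergence definition in SAP 9.1 and Appendix 1 does not fill the gap, because it works on the onset dates of adverse events.

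Size: 44 patients per cohort (SAP 3.4), so one patient is 1/44 = 2.3 percentage points, slightly more if fewer have a post-baseline value. The documents give no rate p of baseline grade 3–4 values. Taking p from 1% to 10% as an assumption, with persistence and no drug effect, the expected number wrongly counted per cohort for one parameter is 44p and the chance of at least one is 1 − (1 − p)^44:

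| p (assumed) | Expected per cohort | Chance of at least one |
|---|---|---|
| 1% | 0.44 | 36% |
| 2% | 0.88 | 59% |
| 5% | 2.2 | 90% |
| 10% | 4.4 | 99% |

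A rule requiring worsening counts none of these patients. Entry limits make the low end more plausible for the tests they cover.

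**2. Shift summary.** Of the three outputs in Protocol 9.4.2.2, SAP 9.2 specifies the graded counts and the changes from baseline but not the shifts. Protocol 9.4 gives the SAP precedence on analysis details, so its silence matters.

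**3. Vital signs and ECG.** Post-baseline values that can be flagged, from the test values tried (pulse 35, 55, 75, 105, 150; temperature 34.8, 36.8, 38.1, 40.5):

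| Baseline | Rule read literally | Rule skipped as inapplicable |
|---|---|---|
| Pulse 55 | none | 35, 55, 105, 150 |
| Pulse 105 | none | 35, 55, 105, 150 |
| Temperature 38.1 | none | 34.8, 38.1, 40.5 |

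Read literally, 55 to 150 is missed; with the rule skipped, 55 to 55 is flagged. The SAP does not choose between these readings.

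For the graded measures:

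| Measure | Baseline grade 1 | Baseline grade 2 | Top category |
|---|---|---|---|
| Systolic | 130: flags 150, 170 | 150: flags 170 | 170: none |
| Diastolic | 85: flags 95, 100 | 95: flags 100 | 100: none |
| Observed QTc | 460: flags 490, 510 | 490: flags 510 | 510: none |

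The exclusion in Protocol 5.2 admits a screening systolic of 160 to 180 and a diastolic of exactly 100, both in the top category, so a change from 165 to 200 would not be flagged. For QTc the gap is mostly closed at entry, because a confirmed value above 500 msec is excluded.

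**The case against.** The strongest reply is that little information is lost. Laboratory and vital-sign changes from baseline and most extreme change are summarised, all values are listed, and the protocol has clinically significant abnormal vital signs and clinically relevant laboratory changes recorded as adverse events (8.4.3, 8.4.5). Only grades 3 and 4 are tabulated, so a miscount needs a patient who entered at that level, and Protocol 5.2 caps baseline ALT, bilirubin, HbA1c and fasting glucose. All of this stands. It limits the impact without making the label correct, and the caps do not cover the other chemistry, haematology and urinalysis tests.

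A reader might go further and infer three things that the documents do not support:

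- **That patients abnormal at baseline can never be flagged on vital signs.** This is false for blood pressure and observed QTc at baseline grades 1 and 2. For pulse and temperature the rule is undefined rather than plainly exclusionary. SAP 9.3.3 presents high and low values separately and lets a patient count in both, which leans towards counting by direction, but it does not say how baseline enters.
- **That the SAP abandons the shift tables.** It is silent. SAP Section 1 places the table shells in a separate document, which was not available and may contain them.
- **That the SAP ignores laboratory baselines altogether.** The missing comparison is confined to the toxicity counts.

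**Conclusion.** The concern holds in limited form. The laboratory counts called treatment-emergent carry no baseline condition, so unchanged (or improved but still grade 3) values are counted. The SAP text does not specify the promised shift summary and does not declare its absence. The baseline rule in SAP 9.3 cannot be applied to pulse and temperature as written, and cannot flag further worsening in a patient who starts in the top blood-pressure or QTc category.

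The impact is modest. Each misclassified patient moves a cohort rate by about 2.3 points; how many there would be depends on a baseline grade 3–4 rate that the documents do not give, and the 1% to 10% range used here is an assumption. These are descriptive tables with no hypothesis test attached. The point is still worth settling before unblinding, because two programmers following the SAP could produce different pulse and temperature tables.

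**What to change.** **SAP 9.2.** Count a laboratory toxicity as treatment-emergent only if the worst post-baseline grade, or limit-multiple band, exceeds the baseline one. State how a missing baseline is handled, since the present denominator does not require one. Add the protocol's shift table across all grades, which also shows new grade 1 and 2 changes.

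**SAP 9.3.** Apply the baseline rule by direction for pulse and temperature: count a high value unless the baseline was high, and a low value unless the baseline was low. This captures 58 to 110. It does not capture 58 to 40, and a shift table on the existing categories would not show that change or systolic 165 to 200, because both stay in one category. For patients abnormal in the same direction at baseline, or in the top blood-pressure or QTc category, report how many there are and their most extreme change from baseline.

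**Cost.** A few sentences in the SAP and a few extra descriptive tables from data already collected. No test, sample size or trial procedure changes.

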9.3. Other Safety Evaluations

For electrocardiogram and vital signs results, Marked Abnormality will be defined in the following sections. Should a patient have a Markedly Abnormal result at baseline, only those

Sponsor: Boston Pharmaceuticals, Inc.
Protocol Number: BOS-589-201
Version and Date: Version 1.2 12NOV2020

post-baseline results that are at least 1 grade more extreme than the baseline grade will be considered as a Marked Abnormality.

9.3.1. 12-Lead Electrocardiogram

12-lead electrocardiograms (ECGs) will be assessed as specified in the Schedule of Activities in Section 1.3 of the protocol. The following ECG parameters will be collected: PR interval (milliseconds [msec]), QRS interval (msec), QT interval (msec), QT interval corrected for heart rate (QTc) (msec), and Ventricular Rate (beats/min). ECG parameters and ECG evaluation will come directly from the database and will not be calculated during analysis.

Observed values and changes from baseline for ECG parameters will be summarized at each scheduled visit (Screening and Day 29/ Early Termination) by cohort and overall.

Observed and change from baseline values on Day 29 in QTc status categorized as markedly abnormal (defined in the table below) or not will be summarized.

QTc Measure	Markedly Abnormal Criteria
Observed	450–480 msec, inclusive [CTCAE grade 1] 481–500 msec, inclusive [CTCAE grade 2] > 500 msec [CTCAE grade 3 or higher]
Change from Baseline	31–60 msec, inclusive, increase from baseline >60 msec increase from baseline

If triplicate measures were taken at a single time point, the average will be summarized. All ECG data will be presented in a by patient data listing for all enrolled patients. Measures meeting the markedly abnormal criteria will be flagged in the listing.

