4.1.4 Number of Sites

Up to 66 sites in the United States may participate in this study.

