11. Patient has a history of significant hypersensitivity, intolerance, or allergy to any drug compound, food, or other substance, unless approved by the Investigator.

Laboratory Assessments

12. Fecal calprotectin > 150µg/g (CCI [REDACTED]).
13. Hemoglobin A1c level ≥ 8.0% or a confirmed fasting plasma glucose level ≥ 180 mg/dL.
14. Confirmed alanine aminotransferase (ALT) > 2x upper limit of normal (ULN).
15. Confirmed total bilirubin > ULN, unless the patient has a documented history of Gilbert's syndrome.
16. Confirmed QT interval corrected by Fridericia's formula (QTcF) or QT interval corrected by Bazett's formula (QTcB) > 500 msec.
17. Evidence of active hepatitis B virus (HBV) infection, based on a positive hepatitis B surface antigen (HBsAg) screen.
18. Evidence of hepatitis C virus (HCV) infection based on a positive HCV antibody screen. Patients with a positive HCV antibody at screening may be eligible if confirmatory testing (i.e., Recombinant Immunoblot Assay [RIBA], or HCV RNA viral load) provided by the study site is negative. Patients who have been successfully treated for HCV are eligible if an undetectable HCV viral load at least 6 months after completion of treatment can be demonstrated.
19. Human immunodeficiency virus (HIV)-1 or HIV-2 antibody positive.

Prior/Concomitant Therapy

20. Within 14 days of randomization, patient has used either of the following:
 - 5-hydroxytryptamine (5-HT)₃ or 5-HT₄ receptor antagonists (e.g., alosetron, ondansetron, or ramosetron);
 - Eluxadoline;
 - Any of the strong inhibitors of P-glycoprotein listed in [Appendix 4](#).
21. Within 14 days of randomization, patient has used any of the following:

- Loperamide; (Note: loperamide can be used during the study as rescue medication based on protocol specified guidelines [see [Section 6.7.1](#)]);
- Bile acid sequestrants such as cholestyramine, colestipol, or colesevelam*
- Aspirin or aspirin-containing medications (> 325 mg of aspirin per day) or nonsteroidal anti-inflammatory drugs, when taken specifically for the symptoms of IBS;
- Narcotic- or opioid-containing agents;
- Cannabis-containing products;
- Docusate;
- Enemas;
- GI preparations (including antacids containing aluminum or magnesium, antidiarrheal agents, antispasmodic agents, bismuth, peppermint oil, IBgard, FDgard, or prokinetic agents).

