8.4.4 Electrocardiograms

Single 12-lead ECGs will be performed at the timepoints specified in the Schedule of Activities ([Section 1.3](#)) and before any blood sample collection. Electrocardiogram interval measurements and interpretation (normal, abnormal not clinically significant, abnormal clinically significant) will be recorded in the source document. Any clinically significant change in ECG interpretation will be recorded as an AE (see [Section 8.5](#)).

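### SAP 9.3.1 names no QTc correction formula and rules out deriving one, so a QTc flag can depend on the formula recorded as well as on the patient

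*SAP*

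**What the plan says.** SAP 9.3.1 (version 1.2; versions 1.0 and 1.1 read the same here) lists the ECG variables, ending with "QT interval corrected for heart rate (QTc) (msec), and Ventricular Rate (beats/min". No correction formula is attached to QTc. The section then says that "ECG parameters and ECG evaluation will come directly from the database and will not be calculated during analysis".

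Fixed limits are applied to that variable. The lowest observed band is "450–480 msec, inclusive [CTCAE grade 1", followed by 481–500 and above 500 msec. The lowest change band is "31–60 msec, inclusive, increase from baseline", followed by more than 60 msec. The introduction to SAP 9.3 adds that a patient already markedly abnormal at baseline counts afterwards only if the later result is at least one grade worse.

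Apart from its abbreviation list, the protocol names formulas only in exclusion criterion 16 (section 5.2): "Confirmed QT interval corrected by Fridericia's formula (QTcF) or QT interval corrected by Bazett's formula (QTcB) > 500 msec". Section 8.4.4 says "Single 12-lead ECGs will be performed at the timepoints specified in the Schedule of Activities" and has the interval measurements entered in the source document; it states neither a formula nor a central reading. Section 9.4.2.3 says only that ECG data are listed and summarized. The Schedule of Activities places ECGs at Screening and at Day 29/Early Termination. On sites, section 4.1.4 says "Up to 66 sites in the United States may participate in this study".

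**The concern.** Bazett and Fridericia give the same value only at 60 bpm and diverge as the rate moves away from it. If the database holds whatever each site's machine or reader supplied, one cut-off is applied to two different quantities. Each patient has a single post-baseline ECG, so nothing within the patient averages this out.

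There is a second problem that needs no mixing. If every value were Bazett, a change in heart rate between the two visits would move QTc by itself.

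Safety is a primary objective, and the markedly-abnormal table is the only planned categorical look at QTc. QT and ventricular rate are both collected, so a uniform value is available; the SAP sentence is what bars deriving it.

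**Working it through.** The documents give no QTc figure to reproduce, so the check is the size of the formula gap against the SAP's own limits.

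**Inputs.** From SAP 9.3.1: flags at 450 msec (observed) and 31 msec (increase). From SAP 9.3.3: pulse is flagged below 60 and at 100 or above, so 60 to just under 100 bpm is the range the plan treats as unremarkable. Assumption, not in the documents: QTcF between 380 and 450 msec.

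**Formulas.** With RR = 60/HR, QTcB = QT/RR^(1/2) and QTcF = QT/RR^(1/3). Hence QTcB/QTcF = (HR/60)^(1/6), and the gap is QTcF × [(HR/60)^(1/6) − 1].

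Direct check: QT 360 msec at 80 bpm gives QTcB 415.7 and QTcF 396.2, a gap of 19.5. The ratio formula gives 396.2 × 0.0491 = 19.5.

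**QTcB minus QTcF (msec)**

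| HR (bpm) | Ratio | QTcF 380 | 400 | 420 | 450 |
|---|---|---|---|---|---|
| 50 | 0.9701 | −11.4 | −12.0 | −12.6 | −13.5 |
| 60 | 1.0000 | 0 | 0 | 0 | 0 |
| 70 | 1.0260 | 9.9 | 10.4 | 10.9 | 11.7 |
| 80 | 1.0491 | 18.7 | 19.6 | 20.6 | 22.1 |
| 90 | 1.0699 | 26.6 | 28.0 | 29.4 | 31.5 |
| 100 | 1.0889 | 33.8 | 35.5 | 37.3 | 40.0 |

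**Observed cut-off.** QTcB reaches 450 when QTcF = 450/(HR/60)^(1/6): 438.6 at 70 bpm, 428.9 at 80, 420.6 at 90 and 413.3 at 100. A patient with QTcF 429 at 80 bpm is therefore flagged under Bazett and not under Fridericia.

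**Change cut-off.** The gap equals 31 msec at HR = 60 × [(QTcF + 31)/QTcF]^6: 96.1 bpm at QTcF 380, 93.9 at 400, 92.0 at 420 and 89.5 at 450. At 70–80 bpm the gap is about 10–22 msec, roughly one third to 70% of the flag. A false change flag from mixing alone also needs Fridericia at Screening and Bazett at Day 29 in the same patient.

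**Bazett at both visits, QTcF held constant.** At QTcF 400, 70 to 90 bpm adds 17.6 msec, 60 to 90 adds 28.0, and 60 to 100 adds 35.5. At QTcF 415, 60 to 90 adds 415 × 0.0699 = 29.0. The 60-to-90 shift falls just short of the 31 msec flag.

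**Effect of the baseline-grade rule.** Suppose the rate is 80 bpm at both visits and QTcF rises from 430 to 452. By Fridericia the patient is newly at grade 1. By Bazett the values are 430 × 1.0491 = 451.1 and 452 × 1.0491 = 474.2, grade 1 at both visits, so no observed-value flag is counted. The formula can therefore remove flags as well as add them.

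**The case against.** The strongest reply is that mixing is conjecture. Exclusion 16 sets an eligibility limit and may simply mean that both corrections are available. The eCRF, any ECG manual and the mock shells (which the SAP keeps in a separate document) are not supplied, and any of them could fix the formula. The sentence about not calculating ECG parameters is a data-source rule; it does not show that the stored values are heterogeneous. All of this stands. A reader might infer that formulas were in fact mixed, and the documents do not support that.

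A reader might also infer that the formula gap is generally about as large as the change flag. It is not: that holds only near 90–100 bpm, and the upper end of that range is where the SAP itself starts to flag pulse.

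Thirdly, a reader might infer that the table would present formula differences as a drug effect. Allocation is blinded and stratified by site, so a site's formula cannot depend on treatment. With 132 patients over up to 66 sites the average could be as low as 132/66 = 2 per site, fewer than the three arms, so within-site balance is not assured, but any imbalance would be a matter of chance. If all values were Bazett, a bias would need a cohort difference in heart rate; protocol 2.2.3.2 reports no drug-related clinically significant change in vital signs or ECGs in the earlier healthy-volunteer study.

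There are safeguards too. No test on QTc is planned, placebo is shown alongside, uncorrected QT and ventricular rate are summarized and listed, and protocol 8.4.4 sends clinically significant ECG changes to AE reporting. These limit the harm. They do not correct the categorical table, and balanced misclassification still blurs it.

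**Conclusion.** The point holds as a gap in specification with a cheap remedy. The SAP flags an undefined QTc and bars the uniform derivation that its own data allow, while the protocol recognizes two formulas and nothing supplied requires one of them across sites or visits.

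Within the assumed QTcF range, the choice of formula matters mainly for the observed-value bands, where ordinary heart rates are enough to cross 450 msec. For the change bands it matters only at high rates combined with a switch of formula within one patient. If Bazett is used throughout, changes in heart rate become the issue instead; that calculation takes a constant QTcF as its reference.

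The expected consequence is misclassification and noise in a descriptive safety table. The primary efficacy analysis is unaffected. If the eCRF or an ECG manual already fixes one formula, mixing drops out, and what remains is that the SAP should name it and, if it is Bazett, deal with the dependence on heart rate.

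**What to change.** In SAP 9.3.1, exempt QTc from the no-calculation sentence and add:

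*QTcF will be derived for every ECG as QT/(60/VR)^(1/3) from the recorded QT and ventricular rate and used for all observed, change and markedly-abnormal QTc summaries; the QTc as recorded, with its formula where known, will be listed.*

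The cost is one derived variable and no new data. The downside is that some analysis values may differ from those the site recorded, which is why the recorded value stays in the listing. With one formula at both visits the between-formula gap is zero at any heart rate. The documents do not designate a primary formula, so Fridericia is a choice: either formula would end mixing, but Fridericia's smaller exponent also avoids the rate-driven shifts shown above for Bazett. The change should be made before database lock and unblinding. It leaves the eligibility criterion untouched.
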